3.1.2 Extension part

The Extension part consists of 2 periods; **Double-blind loading dose period** and **Open-label treatment period**.

The **Double-blind loading dose period** will be applicable for patients who complete the Double-blind treatment period. All patients will receive ofatumumab 20 mg sc at Week 24; the Extension part starts with the injection of the Week 24. Patients randomized to ofatumumab in the Double-blind treatment period will receive the matching placebo sc at Week 25 and 26. Patients randomized to placebo in the Double-blind treatment period will receive ofatumumab 20 mg sc at Week 25 and 26. All patients will receive the study drug in a double-blind manner at Week 25 and 26.

The **Open-label treatment period** will begin at Week 28 and all patients will receive open-label ofatumumab 20 mg sc every 4 weeks in this period. This period will continue until the last patient is transferred to a planned umbrella extension study (under separate protocol requiring another informed consent).

Patients who prematurely discontinue study treatment will have their EOS visits as soon as possible and will be followed up for safety in the Safety FU period ([Section 3.1.3](#)) for a minimum of 36 weeks ([Table 6-2](#)). After study drug discontinuation, during Core or Extension parts, patients may initiate alternative MS therapy according to local standard of care if clinically indicated (see [Section 5.6.2](#)).

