The MRI technician will be responsible for:

- Familiarization with the MRI manual procedures and the study specific MRI protocol
- Performance of a "dry" or "dummy" run using the MRI parameters outlined by the MRI protocol
- Performance of high-quality MRI scans using the study specific parameters stored in the designated MRI scanner for the duration of the study
- Submission of the MRIs in the appropriate format to the central MRI reader immediately upon completion

Radiologist/Neurologist

The local radiologist/Neurologist will be responsible for:

- Reviewing each MRI scan performed for the study patients and contacting the Investigator in case of unexpected or safety-related findings detected on the MRI scan

6 Visit schedule and assessments

[Table 6-1](#) lists all of the assessments and indicates with an "x" when the visits are performed.

Patients should be seen for all visits on the designated day per the schedule of assessments, or as close to it as possible within the visit windows. Missed or rescheduled visits should not lead to automatic discontinuation.

In case a visit is performed outside the schedule, subsequent visits shall be performed in keeping with the original visit schedule (one month is defined as 28 calendar days). In addition to the planned visits, patients may have unplanned visits due to a MS relapse, an acute illness of undetermined cause, for other reasons, or at the discretion of the Investigator. Data collected during unplanned visits will be recorded in the unplanned visit CRFs.

At Week 24, all assessments required for the Core part MUST be completed prior to the first study drug administration for the Extension part.

In the Extension part, patients will be asked to complete a diary to record information pertinent to study drug administration (including date and time of sc injections) and home pregnancy testing (date and results) for females of childbearing potential. The patient is requested to bring the completed diaries with them to each visit and the Investigator/Study Nurse/Study Coordinator must review these for completeness and for potential AEs, injection related reactions, study drug interruptions etc. and record information obtained from the diaries on the relevant CRFs.

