- No MRI (with Gd-enhancement) should be performed while a patient is on steroid therapy for relapse and within the following 14 days upon termination of steroid therapy.

[figure not shown]
As a result of these restrictions, MRI scheduling can be adjusted accordingly. In case a visit is performed outside the visit window, any subsequent visits should be performed according to the original visit schedule.

Scanning

All sequences/scans will be performed according to the institute MRI manual.

Sequences include T1 hypointense images (with and without contrast medium, gadolinium-DTPA), T2-weighted images and brain volume will be performed.

The contrast medium may occasionally cause nausea and vomiting. Allergic reactions may also occur very rarely and, in extremely rare instances, can be potentially serious and require immediate anti-anaphylactic treatment.

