2.1.1 General definitions

Study drug/treatment refers to the investigational drug Ofatumumab and placebo.

“Date of Cut-off 2” is expected as the date the last patient completes all assessments at Week 48 visit. If the last patient discontinues from the study prior to Week 48 visit, “date of Cut-off 2” is the last patient's last visit.

Date of first administration of study drug/treatment, or first date of study drug/treatment, is defined depending on the analysis purposes.

- For Cut-off 1 analysis and Cut-off 2 and final *efficacy* analysis, it refers to the date when the first dose of randomized treatment is administered.
- For Cut-off 2 and final *safety* analysis, it refers to the date when the first dose of ofatumumab is administered.

Date of last administration of study drug/treatment, or last date of study drug/treatment is defined by analysis time point.

- For Cut-off 1 analysis, it refers to the date when the last dose of randomized treatment is administered up to Week 24 visit.
- For Cut-off 2 analysis, it refers to the date when the last dose of treatment is administered up to the date of Cut-off 2.
- For final analysis, it refers to the date when the last dose of treatment is administered up to EOS visit.

Study day is defined as: if after first date of study drug, then (Study Day) = (Date) – (first date of study drug) +1; if before first date of study drug, then (Study Day) = (Date) – (first date of study drug); Study Day 1 is defined as the date of the first administration of study drug; there is no Study Day 0.

Duration of an event is calculated as (event end date) – (event start date) +1.

1 month is counted as 30 days unless otherwise specified.

Baseline is defined for each cut-off analysis.

- For Cut-off 1 analysis, and Cut-off 2 and final *efficacy* analysis, baseline is defined as the last non-missing result before or on the first date of study drug.
- For Cut-off 2 and final *safety* analysis, definition of baseline depends on each patient's treatment course in the study
 - For a patient continuously having ofatumumab across Core and Extension parts, baseline is defined as the last non-missing result before or on the first date of study drug.
 - For a patient switching the treatment from placebo to ofatumumab when entering the Extension part, baseline is defined as the dose date of ofatumumab at Week 24. *For analysis on vital signs*, the baseline is defined as *the pre-dose measurement* at Week 24.

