On-treatment period is defined as the one between the first date of study drug and 30 days after the last date of study drug. The on-treatment definition applies to efficacy analyses only.

“Safety cut-off” is defined as 100 days after the last dosing date of the study drug.

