2.2 Analysis sets

Full analysis set (FAS): The FAS comprises all randomized subjects with assigned treatments. Subjects will be analyzed according to the randomized treatment assignment following the intention-to-treat (ITT) principle, even if they actually received no or a different treatment.

The FAS will be used for the summary of demography and baseline characteristics and all efficacy analyses.

Extension FAS (EFAS): The EFAS will include all FAS subjects who received at least one dose of ofatumumab during Extension part. Analyses on EFAS will include *all* available efficacy assessments of the Core and Extension parts.

Per-protocol set (PPS): The PPS is a subset of FAS, consists of all randomized subjects who take at least one dose of study medication and have no major protocol deviations that could confound the interpretation of analyses conducted on the FAS. Major protocol deviations will be determined according to the pre-defined protocol deviation criteria before treatment unblinding (e.g. non-compliance for a large proportion of the time in study). For analyses performed on the PPS, only on-treatment assessments will be used.

The PPS will primarily be used for the supportive analyses of the primary efficacy variable.

Safety set (SAF): The SAF set includes all subjects who received at least one dose of study medication. Subjects will be analyzed according to the actual treatment received. The Safety Set will be used for all safety analyses for Cut-off 1 analysis.

Extension Safety set (ESAF): The ESAF set includes all subjects who received at least one dose of ofatumumab during Extension part. Subjects will be analyzed according to the actual treatment received. The Extension Safety Set will be used for all Cut-off 2 and final safety analyses. Analyses on ESAF will include safety assessments *only under ofatumumab treatment during the Core and Extension parts*.

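### The SAP's 30-day on-treatment window is shorter than the allowed gap from the Week 20 dose to the Week 24 scan, so the per-protocol repeat of the primary analysis drops some late Week 24 scans from patients who never stopped treatment

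*SAP*

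**What the plan says.** SAP 2.1.1 defines the window: "On-treatment period is defined as the one between the first date of study drug and 30 days after the last date of study drug". It adds: "The on-treatment definition applies to efficacy analyses only". For the last date of study drug at Cut-off 1, the same section states that "it refers to the date when the last dose of randomized treatment is administered up to Week 24 visit".

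Protocol 3.1.2 assigns the Week 24 injection to the next part: "the Extension part starts with the injection of the Week 24". Protocol Section 6 fixes the order of events on that visit: "At Week 24, all assessments required for the Core part MUST be completed prior to the first study drug administration for the Extension part".

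SAP 2.2 then applies the window to the per-protocol set (PPS): "For analyses performed on the PPS, only on-treatment assessments will be used". SAP 2.5.4 names the PPS repeat of the primary analysis as its sensitivity analysis, to be done at Cut-off 1. It specifies no other, although it leaves room for additions before database lock. SAP Section 4 records that time to first confirmed relapse was removed from that role.

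Nothing in either document exempts patients who complete the Core part or extends the window to the Week 24 scan.

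**The concern.** The 30-day limit fits a patient who is exactly on schedule, with two days to spare. It does not fit the timing tolerances that the protocol and SAP themselves allow. A patient with no missed dose can have a Week 24 scan that counts in the primary analysis but is classed as off-treatment in the PPS repeat.

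Lateness of this kind does not remove the patient from the PPS: SAP 5.6 lists no visit-timing deviation among its exclusions. The patient stays in with three scans instead of four. SAP 2.5.4 presents the PPS repeat as an analysis of on-treatment data, and the rule would make it something slightly different: on-treatment data minus late final scans. A difference between the FAS and PPS results would then be harder to read.

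**Working it through.** **Plan's own figure.** SAP Section 3 states more than 90% power with 60 patients (2:1), 1.0 versus 0.08 lesions per scan, dispersion 4.5, one-sided alpha 0.025 and 10% dropout. The claim is not in dispute; I use it to size the information loss. For a negative binomial Wald test on the log rate ratio with t scans per patient:

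Var = (1/(t × 1.0) + 4.5)/n₀ + (1/(t × 0.08) + 4.5)/n₁

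With t = 4 and 18/36 patients after dropout, Var = 4.75/18 + 7.625/36 = 0.476. Power = Φ(2.526/√0.476 − 1.96) = 95.6%. With 20/40 it is 97.1%. Both agree with the plan.

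**Anchor.** The Week 24 injection belongs to the Extension part and follows all Core assessments, so the last randomised dose is at Week 20.

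**Timing inputs**
- Week 20 dose: Day 140 ± 3, so Days 137 to 143 (Protocol 5.5.4; Table 6-1, footnote 17).
- Week 24 visit, including MRI: Day 168 ± 7, so Days 161 to 175 (Protocol Table 6-1).
- Week 24 injection: ± 3 days, so Day 171 at the latest (Table 6-1, footnote 17).
- SAP window for the Week 24 MRI: Days 155 to 182 (SAP Table 2-1).

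**Gap = scan day − Week 20 dose day, compared with 30.** On schedule it is 168 − 140 = 28, inside the window. The largest gap depends on how the tolerances are combined:

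| Reading | Scan days | Largest gap | Combinations over 30 days |
|---|---|---|---|
| ± 3 days read as a tolerance on the 28-day interval, scan no later than the injection | – | 28 + 3 = 31 | – |
| Scan precedes an injection given by Day 171 | 161–171 | 171 − 137 = 34 | 10 of 7 × 11 = 77 (13%) |
| Visit window alone | 161–175 | 175 − 137 = 38 | 35 of 7 × 15 = 105 (33%) |
| SAP MRI window | 155–182 | 182 − 137 = 45 | 84 of 7 × 28 = 196 (43%) |

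Every reading exceeds 30. With the Week 20 dose exactly on Day 140, scans on Days 171 to 175 fall outside.

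**Could the Week 24 injection be the anchor?** That would remove the problem, but placebo patients receive ofatumumab at that injection, so it is not a dose of their randomised treatment. It would also make Core exposure under the SAP 2.4.1 formula 168 − 1 + 31 = 198 days (28.3 weeks), against 140 − 1 + 31 = 170 days (24.3 weeks) with Week 20 as the last dose.

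**A related mismatch.** The same exposure formula subtracts nothing when injections are 31 days apart. A scan taken on that 31st day, before the injection, is nevertheless outside the on-treatment period.

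**Information loss (18/36 patients).** If a third of patients lost the Week 24 scan (mean 3.67 scans), power would be 95.2%. If all did (t = 3), Var = 4.833/18 + 8.667/36 = 0.509 and power would be 94.3%, against 95.6%.

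**Steroid-deferred scans.** Protocol 6.4.3 bars MRI during relapse steroids and for 14 days after, and says: "As a result of these restrictions, MRI scheduling can be adjusted accordingly". With a course of up to 5 days (Protocol 5.5.6), about 19 days matter. At the planning relapse rates (SAP 3.2), expected relapses in such a window are 0.4 × 20 × 19/365.25 = 0.42 on placebo and 0.16 × 40 × 19/365.25 = 0.33 on ofatumumab, or 0.75 in total.

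**The case against.** The strongest reply is that the effect is small and confined. The FAS analysis carries no on-treatment restriction. Affected patients stay in the PPS with their earlier scans, and the log(number of scans) offset handles unequal scan counts. That stands, and the power figures bear it out.

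The reply is also right about compliance. A reader might take 38 days and 33% as describing fully compliant patients. But the scan must precede the Week 24 injection, which is itself due within 3 days. A patient within both the visit and dosing windows has a gap of at most 34 days, and the matching share is 13%. Both shares treat every allowed day as equally likely; the documents give no data on actual timing.

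A reader might further infer that steroid deferrals make the loss fall mainly on placebo. The per-patient relapse rate is higher there, but 2:1 allocation brings the expected counts close together (0.42 and 0.33), with under one patient in total. Protocol 6.4.3 also asks that a scan due within 14 days of starting steroids be done first, and SAP 2.5.2 already excludes scans within 14 days after steroids. Differential loss is possible, but the documents do not support calling it a material bias.

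What the reply does not remove is the rule itself: no reading consistent with the Week 20 anchor brings the allowed gap down to 30 days.

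**Conclusion.** The point holds as a defect in a supportive analysis. As written, the SAP drops late Week 24 scans of patients still on treatment from the only specified sensitivity analysis of the primary endpoint. The excess over 30 days is 1 to 8 days under the protocol's tolerances and up to 15 under the SAP's MRI window. The conclusion rests on taking the Week 20 injection as the Cut-off 1 anchor, which is the natural reading but is not stated outright.

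It would be tempting to conclude that the primary result is at risk or that a third of patients lose a scan. Neither follows: the FAS analysis is untouched, a patient on schedule keeps all four scans, and the percentages count calendar combinations. No change in the PPS estimate or its direction has been shown. The change is worth making because the rule discards valid endpoint data and is cheap to correct.

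**What to change.** Add to SAP 2.1.1 that the Cut-off 1 anchor is the last Core dose. For patients who did not discontinue study drug in the Core part, state that the on-treatment period for MRI runs through the Week 24 Core scan, taken before the Week 24 injection. Keep the 30-day rule for patients who discontinued; lengthening it for them is not needed and would add off-drug time. Limit the wording to MRI, because SAP 2.4.1 uses the on-treatment duration as the denominator for compliance, and compliance below 80% excludes a patient from the PPS.

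The SAP history suggests that this version post-dates the Cut-off 1 lock. If so, report by arm how many Week 24 scans the 30-day rule removed, and rerun the PPS analysis with the corrected window, labelled as such. The cost is one sentence plus, after lock, a small amount of extra analysis. Dosing, visits and data collection do not change.

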2.1.2 Visit windows for data analysis

Visit windows for data analysis will be used in both efficacy and safety data summaries by visit. Visit windows define a time period around the targeted visit date as defined in the evaluation schedule of the clinical study protocol. Visit windows are non-overlapping, and defined without

gaps between consecutive visit windows. The width of visit windows may vary over the course of the study period.

Baseline assessments are defined in [Section 2.1.1](#) and do not require a visit window.

The purpose of visit window is to analyze data based on the actual study days (rather than the nominal visits). E.g., if a patient's Week 4 visit is delayed, then it is possible that the Week 4 data be re-aligned to visit window of Week 8 and be summarized under Week 8.

For efficacy analyses, all nominal visits excluding unscheduled visits will be mapped into one of the defined visit windows. [REDACTED]

For safety analyses, all visits (scheduled and unscheduled) will be mapped to visit windows. Safety data from unscheduled visits may be reported separately if applicable.

It is possible that more than one assessment of a patient fall into a particular visit window. [Section 2.1.2.3](#) deals with the statistical approaches to handle multiple visits in a given visit window.

Tables displaying summary statistics “by visit” will use the term “Visit-window” as column header; this is to remind the reviewer that multiple assessments of a patient might be summarized for one visit. Below tables provide visit windows definitions for applicable parameters. Visit windows will be defined relative to the date of first administration of study treatment assigned in the Core part, or date of first administration of ofatumumab, depending on analysis variables and cut-off time points.

2.1.2.1 Visit windows during core and extension treatment periods

Table 2-1 Visit windows for MRI

Visit-window	Start day	Target day	End day
Week 12	1	84	98
Week 16	99	112	126
Week 20	127	140	154
Week 24 (Cut-off 1)	155	168	182
Week 36	183	252	294
Week 48	295	336	378

Day counts are relative to the first date of study drug in the Core part.

Table 2-2 Visit windows for [REDACTED] EDSS

Visit-window	Start day	Target day	End day
Week 12	1	84	126
Week 24 (Cut-off 1)	127	168	210
Week 36	211	252	294
Week 48	295	336	378
Week 60	379	420	462

Visit-window	Start day	Target day	End day
Week 72	463	504	546
Week x*	x*7-42+1	x*7	x*7+42

*if study goes beyond Week 72, every 12 weeks the same assessments on Week 60 and Week 72 will be performed. X will be a multiple of 12 weeks from Week 84 and beyond.
Day counts are relative to the first date of study drug in the Core part.

Table 2-3 Visit windows for routine lab (including urine), ADA, and Total IgM, IgG levels

Visit-window	Start day	Target day	End day
Week 4	1	28	56
Week 12	57	84	126
Week 24 (Cut-off 1)	127	168	182
Week 28	183	196	224
Week 36	225	252	294
Week 48	295	336	378
Week 60	379	420	462
Week 72	463	504	546
Week x*	x*7-42+1	x*7	x*7+42

*if study goes beyond Week 72, every 12 weeks the same assessments on Week 60 and Week 72 will be performed. X will be a multiple of 12 weeks from Week 84 and beyond.
Day counts are relative to the first date of study drug in the Core part for Cut-off 1 analysis, or the first date of ofatumumab for Cut-off 2 and final analysis.

[figure not shown]

Table 2-5 Visit windows for B-cell counts and T-cell counts: Cut-off 1 analysis

Visit-window	Start day	Target day	End day
Day 2	--	2	--
Day 5	3	5	--
Day 7	6	7	10
Day 14	11	14	21

Visit-window	Start day	Target day	End day
Week 4	22	28	56
Week 12	57	84	126
Week 24 (Cut-off 1)	127	168	182

Day counts are relative to the first date of study drug in the Core part.

Table 2-6 Visit windows for B-cell and T-cell counts: Cut-off 2 and final analysis

Visit-window	Start day	Target day	End day
Week 4	1	28	56
Week 12	57	84	126
Week 24	127	168	210
Week 36	211	252	294
Week 48	295	336	378
Week 60	379	420	462
Week 72	463	504	546
Week x*	$x * 7 - 42 + 1$	$x * 7$	$x * 7 + 42$

*if study goes beyond Week 72, every 12 weeks the same assessments on Week 60 and Week 72 will be performed. X will be a multiple of 12 weeks from Week 84 and beyond.

Day counts are relative to the first date of ofatumumab.

Table 2-7 Visit windows for vital signs: Cut-off 1 analysis

Visit-window	Start day	Target day	End day
Week 8	1	56	70
Week 12	71	84	98
Week 16	99	112	126
Week 20	127	140	168

*if study goes beyond Week 72, every 12 weeks the same assessments on Week 60 and Week 72 will be performed. X will be a multiple of 12 weeks from Week 84 and beyond.

Data collected from Day 1, Day 7, Day 14, Week 4, and Week 24 are collected differently and not re-mapped.

Day counts are relative to the first date of study drug in the Core part.

Table 2-8 Visit windows for vital signs: Cut-off 2 and final analysis

Visit-window	Start day	Target day	End day
Week 12	1	84	126
Week 36	211	252	294
Week 48	295	336	378
Week 60	379	420	462
Week 72	463	504	546
Week x*	$x * 7 - 42 + 1$	$x * 7$	$x * 7 + 42$

Visit-window	Start day	Target day	End day
*if study goes beyond Week 72, every 12 weeks the same assessments on Week 60 and Week 72 will be performed. X will be a multiple of 12 weeks from Week 84 and beyond.			
Data collected from Week 24 are not re-mapped, because they are collected at pre- and post-dose and will not be included in by-visit summary.			
Day counts are relative to the first date of ofatumumab.			

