2.1.3 Nominal visits for ECG analysis

By-visit summary of ECG measurement uses nominal visits.

For Cut-off 2 and final analysis, analysis visits will be based on the treatment course of patients in the study.

- For a patient having ofatumumab treatment across Core and Extension parts, assessments at study visits Week 24 and 48 will be included in the summary of corresponding visits.
- For a patient switching the treatment from placebo to ofatumumab at Week 24, assessments from Week 48 visit will be included *in the summary of Week 24 visit*

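### SAP Table 2-8 leaves Days 127–210 in no vital-sign window, so placebo-to-ofatumumab switchers' study Week 48 visit drops out of any visit-windowed summary

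*SAP*

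**What the plan says.** SAP 2.1.2 gives the general rule for windows: "Visit windows are non-overlapping, and defined without" "gaps between consecutive visit windows. The width of visit windows may vary". For safety data it adds: "For safety analyses, all visits (scheduled and unscheduled) will be mapped to visit windows".

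Table 2-8 in SAP 2.1.2.1 covers vital signs at Cut-off 2 and the final analysis. Its first two rows (window, start, target, end) are "Week 12 1 84 126" and "Week 36 211 252 294". There is no Week 24 row, and the footnote gives the reason: "Data collected from Week 24 are not re-mapped, because they are collected at pre- and post-dose and will not be included in by-visit summary". The day origin is also in the footnote: "Day counts are relative to the first date of ofatumumab".

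Two neighbouring rules treat the same situation differently:

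- Table 2-6 (B- and T-cell counts, same analyses, same day origin) has a Week 24 row running from Day 127 to Day 210.
- SAP 2.1.3 on ECG says: "For a patient switching the treatment from placebo to ofatumumab at Week 24, assessments from Week 48 visit will be included", and it places those assessments under Week 24.

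SAP 2.8.4.2 leaves the pre-/post-injection visits, study Week 24 among them, out of the descriptive by-visit vital-sign summary. The only vital-sign analysis that it expressly repeats at Cut-off 2 is the clinically notable table.

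**The concern.** The footnote reasons in study weeks, but the table counts days from first ofatumumab. The two scales agree only for patients who were on ofatumumab from Day 1. For a switcher, study Week 24 is Day 1 on the table's scale and serves as the baseline. What falls near Day 168 is the study Week 48 visit, which is a routine assessment. The exclusion therefore removes the wrong visit for that group.

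What is at stake is the switchers' vital-sign record after about 24 weeks on drug. Their study Week 28 and Week 36 visits both map to the Week 12 window. A switcher whose latest visit at Cut-off 2 is Week 48 would thus contribute to one window only, and to none near 24 weeks. This matters for the completeness of a safety display. It has no bearing on the primary or secondary efficacy analyses.

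**Working it through.** **Inputs**
- Table 2-8 bounds: Week 12 = Days 1–126; Week 36 = 211–294; Week 48 = 295–378; Week 60 = 379–462; Week 72 = 463–546.
- Window formula in the table's last row: start 7x − 42 + 1, target 7x, end 7x + 42.
- Study day (SAP 2.1.1): date − first date + 1. For Cut-off 2 and final safety analysis, the first date is the first ofatumumab dose.
- Switchers' first ofatumumab dose: study Week 24 (SAP 1.1).
- Visit tolerances (Protocol Table 6-1): Weeks 20, 24, 36 and 48 ±7 days; Week 28 ±3; Weeks 60 and 72 ±14.
- Pre-/post-injection vital signs in the Extension: Week 24 only (Protocol 6.5.2 and Table 6-1 footnote 7).

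**Step 1: reproduce the table.** For x = 36, 48, 60 and 72 the formula returns every printed bound. For x = 12 it gives 43 / 84 / 126, which matches apart from the start, printed as Day 1. For x = 24 it gives 168 − 42 + 1 = 127, target 168, end 168 + 42 = 210. That is the absent row, and it equals the Week 24 row of Table 2-6. The hole is Days 127–210, or 210 − 127 + 1 = 84 days, and it is the only gap in the table.

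**Step 2: place the switchers' visits.** Nominal day = (study week − 24) × 7 + 1. The range allows ±7 days for the Week 24 dose plus the tolerance of the later visit.

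| Study visit | Nominal day | Range | Window in Table 2-8 |
|---|---|---|---|
| Week 28 | 29 | 19–39 | Week 12 |
| Week 36 | 85 | 71–99 | Week 12 |
| Week 48 | 169 | 155–183 | none |
| Week 60 | 253 | 232–274 | Week 36 |
| Week 72 | 337 | 316–358 | Week 48 |

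The whole Week 48 range lies in the hole. To reach a window, the visit would have to be 169 − 126 = 43 days early or 211 − 169 = 42 days late. Protocol Table 6-1 footnote 17 allows only ±3 days for the Week 24 injection; with that figure the range narrows to 159–179.

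**Step 3: place the continuous patients' visits.** Depending on whether Week x is read as day 7x or 7x + 1:
- Week 20 is Day 140 or 141 (range 133–148): no window.
- Week 24 is Day 168 or 169 (range 161–176): no window, as the footnote intends.
- Week 28 is Day 196 or 197 (range 193–200): no window.

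Neither Week 20 nor Week 28 is a pre-/post-injection visit, so the footnote does not cover them.

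**Step 4: patients exposed.** 60 × 1/3 = 20 planned placebo patients. Applying the plan's 10% dropout allowance gives 20 × 0.9 = 18.

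**Step 5: repeat with a Week 24 row of 127 / 168 / 210.** The switchers' Week 48 visit maps to Week 24 over its whole range, and their other visits do not move. Continuous patients' Weeks 20 and 28 also map to Week 24.

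**The case against.** The strongest reply is that the missing row is a disclosed choice, made for a stated reason, in a table whose use at Cut-off 2 is limited.

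- **The exception is deliberate.** This is true for continuous patients. Their study Week 24 measurements are pre-/post-dose and SAP 2.8.4.2 keeps them out of the by-visit summary. It does not carry over to switchers' Week 48.
- **A by-visit summary at Cut-off 2 is not clearly promised.** SAP 2.8.4.2 expressly repeats only the clinically notable table, whereas SAP 2.8.3 names summary statistics among the repeated laboratory outputs. This stands as an ambiguity. Table 2-8, by its title and by its footnote's mention of such a summary, would have little purpose if none were produced.
- **The notable table may be unaffected.** It counts patients, not visits. If all post-baseline values enter, the Week 48 values count. However, SAP 2.1.2.3 draws worst-case tables, notable abnormalities included, from assessments inside a visit window. SAP 2.8.3 lifts the multiple-assessment rules for laboratory tables only. The SAP does not settle which applies to vital signs.
- **Nothing is deleted.** This stands. A reader might infer that the values are discarded altogether, but SAP 2.1.2.3 puts every result in the listings, and SAP 2.8 has clinically significant vital-sign findings reported and analysed as adverse events.
- **The continuous arm loses little.** A reader might count two lost visits for each of 40 patients. That overstates it: Table 2-7 already summarises Week 20 at Cut-off 1. Restoring the row would also yield one value per patient, because SAP 2.8.4.2 averages blood pressure and pulse within a window.
- **Switchers are not limited to three visits by Cut-off 2.** This stands. Cut-off 2 is set by the last patient's Week 48, so those enrolled earlier may also have Week 60 or Week 72 visits, which do map.

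**Conclusion.** Table 2-8 is wrong as written for switchers. Its gap contradicts SAP 2.1.2, its stated reason does not apply to them, and Table 2-6 and the ECG rule handle the same shift in time scale correctly. Every on-schedule study Week 48 vital-sign assessment in the switch group (about 20 planned, about 18 after the dropout allowance) falls outside all windows. Continuous patients' Week 28 values are also unmapped, as are their Week 20 values as far as this table goes.

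The effect is confined to visit-windowed vital-sign summaries, and to the notable table only if the SAP 2.1.2.3 rule is applied to it. The documents do not support saying that the data are lost from the trial, or that a planned Cut-off 2 table is certain to be incomplete. The conclusion assumes that visits keep to the Protocol Table 6-1 tolerances and that Table 2-8 is used as printed. It is a minor point, but a clear one.

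**What to change.** - Add a row to Table 2-8: Week 24, start 127, target 168, end 210, as in Table 2-6.
- Reword the footnote so that it excludes only measurements taken at the nominal study Week 24 visit as pre-/post-dose pairs, in line with SAP 2.8.4.2. Bringing continuous patients' Week 24 pre-dose values into the new row is not needed and would conflict with that section.
- State in SAP 2.8.4.2 that the clinically notable table uses all post-baseline values, whether or not they fall in a window. Also say there whether the descriptive by-visit summary is produced at Cut-off 2.

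The cost is one table row and a few sentences, with no new data. Any vital-sign output already produced on the present windows would need to be rerun.
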